## **Overview**

We are requesting compassionate access to lefamulin for symptomatic patients with *Mycoplasma genitalium* who have failed (a) moxifloxacin and/or (b) other second or third line antimicrobials (e.g., minocycline, omadacycline, other), or when moxifloxacin is contraindicated.

We also request modest funding to cover the costs of prescribing and distributing lefamulin to patients across the US who meet criteria for compassionate access, document treatment outcomes to estimate the efficacy of lefamulin alone and of pre-treatment with doxycycline followed by lefamulin for MG treatment failures, and collect specimens for culture and assessment of minimum inhibitory concentrations (MICs).

## **Background**

Declining efficacy of standard therapies and the emergence of antimicrobial resistance increasingly hinder the management of bacterial sexually transmitted infections (STIs). Although antibiotic resistant *Neisseria gonorrhoeae* (GC) has been classified as an urgent threat by the US Centers for Disease Control and Prevention (CDC) since 2013, the prevalence of antibiotic resistance in *Mycoplasma genitalium* (MG) is dramatically higher and multiple cases of untreatable MG have emerged. In recognition of this, the CDC's *Antibiotic Resistance Threats in the United States, 2019* report includes MG as one of three organisms on a newly created Watch List.

Moxifloxacin is currently recommended as second-line therapy for MG treatment failures, yet fluoroquinolone resistance in the US is already estimated at 12.8% (95% CI 0.4-34.2%). Although pristinamycin and combination therapy with doxycycline and sitafloxacin have shown efficacy in cases of MG treatment failures, neither pristinamycin nor sitafloxacin are available in the US. As a result, US providers' only recourse is to trial older antimicrobials (e.g., minocycline) in cases of moxifloxacin treatment failure or when moxifloxacin is contraindicated. This is not always successful.

Lefamulin is a highly potent novel antimicrobial of the pleuromutilin class that is approved by the FDA for the treatment of Community Acquired Bacterial Pneumonia (CABP). Lefamulin was well-tolerated in Phase II and Phase III studies, and initial *in vitro* studies demonstrated high susceptibility of STI pathogens to lefamulin. Notably, susceptibility of CT (MIC50/90, 0.02/0.04 mg/liter) and GC (MIC50/90, 0.12/0.5 mg/liter) were good, and susceptibility of MG was excellent (MIC range, 0.002 to 0.063 mg/liter for multi-drug resistant strains). Given this high degree of *in vitro* susceptibility and its favorable safety profile, lefamulin holds great promise for MG treatment failures and/or where moxifloxacin is contraindicated. Although the recommended oral dose for CABP is 600mg twice daily for 5 days, MG is a slow growing organism and may require longer durations of therapy. Therefore, we propose to use **lefamulin 600mg orally twice daily for 7 days for** *M. genitalium* **treatment failures with or without pre-treatment with doxycycline 100mg twice daily for 7 days.** 

Diagnostic testing for MG in the US is more limited than in Europe and Australia and only two nucleic acid amplification tests (NAAT) are currently approved by the FDA: the Hologic Aptima MG assay and the Roche TV/MG test. Several large commercial laboratories have also validated and offer their own in-house laboratory developed tests. Neither of the two FDA-approved assays includes the capability to detect macrolide resistance mutations (MRM). The SpeeDx ResistancePlus MG assay, which does have this capacity, is not yet FDA-approved and not available in the US. As such, the resistance-guided therapy approach developed by investigators at the Melbourne Sexual Health Centre is rarely implemented in the US and macrolide resistance is infrequently documented. Instead, US providers infer its presence after treatment failure. Additionally, in recognition of increasing macrolide resistance in STI pathogens, doxycycline is replacing azithromycin as first line therapy for STI syndromes. Many STD clinics in the US now treat first with doxycycline, and then treat empirically with moxifloxacin when MG is detected. Not all MG treatment failures have previously received azithromycin. Therefore, eligibility for compassionate access to lefamulin will be determined on the basis of previous treatment failures.

## **Objective**

To estimate the efficacy of lefamulin for the treatment of symptomatic MG treatment failures and/or where moxifloxacin is contraindicated.

# Study Design

We propose to provide compassionate access to lefamulin and estimate the efficacy of lefamulin in treating antibiotic resistant MG through a coordinating center at the University of Washington (UW). We will enroll a total of 40 symptomatic patients with MG infections who have experienced treatment failure after moxifloxacin and/or other second or third line antimicrobials

or in whom moxifloxacin is contraindicated. Patients will be followed for 42 or 56 days, depending on the regimen they receive.

There is an increasing global trend to pre-treat MG infections with doxycycline to reduce organism load. There have also been several initial reports of treatment failure after a 7-day regimen of lefamulin alone, but successes after a regimen in which patients were pre-treated with doxycycline in the companion study in Melbourne, Australia. Therefore, we propose to also determine if pre-treatment with doxycycline is necessary. To simultaneously assess the efficacy of lefamulin alone (600mg orally twice daily for 7 days), and a regimen incorporating pre-treatment with doxycycline 100mg orally twice daily for 7 days followed by lefamulin 600mg orally twice daily for 7 days), we will randomize the first 20 patients to either Regimen A (lefamulin alone) or Regimen B (pretreatment with doxycycline followed by lefamulin) in a 1:1 ratio.

An interim analysis will be performed after the first 20 patients are enrolled to assess the efficacy of each of these two regimens for futility. Based on the results of this interim analysis, we will make one of three possible decisions:

- If neither of the regimens meet criteria for futility, we will continue randomizing patients to one of the two regimens until we have reached our target sample size of 40 patients (20 randomized per arm).
- If one of the regimens meets criteria for futility but the other regimen does not, we will drop the regimen that met futility criteria and continue to administer the other regimen to the remaining 20 patients for a total of 30 randomized patients in the retained regimen.
- If both regimens meet criteria for futility, we will halt the study and reassess the possibility of using alternative dosing regimens.

Criteria for futility are outlined in the section on sample size on p. 6.

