## **Outcomes**

We will assess one primary outcome and five secondary outcomes.

- Primary Outcome
  - Microbiologic cure defined as a negative Aptima MG test 21-28 days after completing lefamulin
- Secondary Outcomes
  - Microbiologic cure, as defined above, after lefamulin alone compared to microbiologic cure after sequential treatment with doxycycline followed by lefamulin
  - Clinical cure defined as absence of symptoms, absence of visible discharge, and absence of other clinical signs (<5PMNs/hpf on Gram stained smear where available) 21-28 days after completion of the lefamulin
  - Reported adherence to lefamulin (defined by self-reported number of tablets taken)
  - Reported adverse events (defined by self-reported adverse events)
  - Sustained microbiologic cure defined as a negative Aptima MG test 42-47 days after completing lefamulin

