# Sample size

We initially estimated the sample size needed based on the precision around efficacy estimates for lefamulin in a single arm study and estimated that a total of 30 patients with complete data on tests of cure, adherence, and adverse events would provide precision to estimate efficacy  $\geq$ 90% with binomial exact 95% Cl's ranging from 73.5% - 99.9%. Assuming loss to follow-up of up to 30%, **a total of 40 patients will need to be enrolled**.

Because there are fewer people in each arm of a two-arm randomized pilot trial, the statistical power and precision will be somewhat than that estimated for a single arm study. Table 2 compares precision for an arm with 20 randomized persons to one with 30 randomized persons. Even in the case where an arm has only 20 randomized persons, the lower bound of the confidence intervals is >60%, which would still demonstrate benefit.

**Table 2**: Precision around estimated cure rates assuming 40 patients are enrolled and outcome data are available on either 20 participants randomized per arm (if neither regimen meets criteria for futility), or 30 participants randomized to an arm (if one of the regimens meets criteria for futility)

Lefamulin	N=20		N=30	
failures (n)	Estimated cure	95% confidence	Estimated cure	95% confidence
		intervals		intervals
3	85%	62.11 – 96.79	90%	73.5 – 97.9
2	90%	68.30 - 98.77	93%	77.9 – 99.2
1	95%	75.13 – 99.87	96%	82.8 - 99.9

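### If one regimen is dropped, only about 10 of the 30 patients called randomised in the retained regimen are randomised, and nothing keeps the 20 directly assigned patients out of the regimen comparison

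*Combined protocol and SAP*

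**What the plan says.** The Study Design section sets enrolment at 40. For the first stage, "we will randomize the first 20 patients to either Regimen A (lefamulin alone) or Regimen B", in a 1:1 ratio. What follows depends on the interim result:

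- Neither regimen futile: "we will continue randomizing patients to one of the two regimens until we have reached our target sample size of 40 patients", giving 20 per arm.
- One regimen futile: "continue to administer the other regimen to the remaining 20 patients", "for a total of 30 randomized patients in the retained regimen".
- Both futile: the study halts.

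The Table 2 caption in the Sample size section describes the second case in the same terms: "30 participants randomized to an arm (if one of the regimens meets criteria for futility".

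The first secondary outcome (Outcomes) is "Microbiologic cure, as defined above, after lefamulin alone compared to microbiologic cure after sequential treatment with doxycycline followed by lefamulin". The Study Design section gives the reason for having two arms: to find out whether doxycycline pre-treatment is needed. The Data analysis section plans simple proportions with 95% confidence intervals, and the denominator for each outcome is all patients with complete data on it. No section says which patients enter the regimen comparison if an arm has been dropped.

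**The concern.** The plan's own verbs differ between the two cases. When both regimens survive, it goes on randomising. When one is dropped, it administers the other to everyone who follows. Those later patients have no randomised counterpart, so the label is wrong for 20 of the 30.

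The label matters because of the comparison. A reader told that 30 patients were randomised to one arm and 10 to the other would take the contrast as randomised throughout. In fact, any change over calendar time in who is referred, in their previous antibiotics or in how many return test kits would be confounded with regimen. The documents make such change plausible: the Background describes first-line practice moving from azithromycin to doxycycline, and Recruitment describes decentralised referral by individual providers. The later patients also make the comparison look more precise without adding any randomised evidence to it.

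**Working it through.** **Inputs.** From Study Design: 40 enrolled; first 20 randomised 1:1; remaining 20 all given the retained regimen if one is dropped. From Criteria for futility: a regimen is dropped at three or fewer cures in its first 10 patients; reference efficacy 60%. Assumed, not in the documents: the true cure rates, the drift between stages, and the 80% and 30% observed cure rates in the illustration.

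**1. The plan's figure of 30.** 20 × 1/2 = 10, plus 40 − 20 = 20, gives 30. The count reproduces. Randomised: 10/30 = 33%. Directly assigned: 20/30 = 67%. In this case 20 patients are randomised in the whole trial, not 40. Ten per arm is an expectation, since no blocking is described.

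**2. Table 2, N=30.** Exact (Clopper-Pearson) 95% limits for 3, 2 and 1 failures are 73.5–97.9, 77.9–99.2 and 82.8–99.9, as printed. They describe a single proportion and do not depend on randomisation.

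**3. How often exactly one arm is dropped.** With q = P(3 or fewer cures in 10), the probability is q_A(1 − q_B) + q_B(1 − q_A). At 60% true cure q = 0.0548, which agrees with the protocol's 5% after rounding.

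| Assumed true cure, one arm / other arm | q | q | Exactly one dropped |
|---|---|---|---|
| 60% / 60% | 0.0548 | 0.0548 | 10.4% |
| 40% / 60% | 0.3823 | 0.0548 | 39.5% |
| 40% / 80% | 0.3823 | 0.0009 | 38.2% |
| 30% / 60% | 0.6496 | 0.0548 | 63.3% |

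**4. Effect of drift.** If cure in the later 20 differs by d points from the first stage, the pooled estimate from 30, and so the difference between regimens, moves by d × 20/30. That is 6.7 points for d = 10 and 13.3 points for d = 20. With 10 versus 10 it does not move.

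**5. Effect on the interval (illustration).** Newcombe interval from Wilson limits, for 80% cured in the retained arm and 3/10 in the dropped arm. Wilson limits are 0.627–0.905 for 24/30, 0.490–0.943 for 8/10 and 0.108–0.603 for 3/10.

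- 24/30 v 3/10: lower 0.50 − √[(0.800 − 0.627)² + (0.603 − 0.300)²] = 0.15; upper 0.50 + √[(0.905 − 0.800)² + (0.300 − 0.108)²] = 0.72.
- 8/10 v 3/10: lower 0.50 − √[(0.800 − 0.490)² + (0.603 − 0.300)²] = 0.07; upper 0.50 + √[(0.943 − 0.800)² + (0.300 − 0.108)²] = 0.74.

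The difference is 50 points both times. The interval is 57 points wide with the directly assigned patients and 67 without.

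**6. Selection by the futility stop.** Let both regimens truly cure 60%, with exactly one dropped and no drift. The dropped arm then has an expected observed cure of 27.4%, and the retained arm's first 10 have 61.9%. The retained 30 have (10 × 61.9 + 20 × 60)/30 = 60.6%. The spurious gap is 60.6 − 27.4 = 33.2 points for 30 versus 10, and 34.5 points (from unrounded values) for 10 versus 10. Restricting to concurrent patients therefore does not remove this bias.

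**The case against.** The objective is to estimate the efficacy of lefamulin, the sample size rests on single-arm precision, and the N=30 limits in Table 2 need no randomisation. Calling the 30 patients treated rather than randomised changes no planned number. This stands. A reader might infer that the precision claimed for 30 patients is invalid; the documents do not support that.

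The plan states no test, significance level or power for the regimen comparison. A reader might infer that adding the later patients would reverse a conclusion. Nothing in the plan supports that either: it reports intervals, and both illustrative intervals exclude zero. The damage is a contrast that is partly non-randomised and looks too precise.

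The Data analysis denominator sentence was written about missing data, as its example shows, so the 30 versus 10 comparison is what follows from silence rather than an explicit instruction. That is fair, but its wording includes everyone and nothing elsewhere excludes the later patients.

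The drift is hypothetical, and 6.7 points is small beside an interval about 60 points wide. That is true of its size. It is still an avoidable bias, and more patients do not shrink it.

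The problem arises only if exactly one arm is dropped, and by then the decision to drop has been taken. This limits its weight. Even so, the comparison remains a listed outcome, and the protocol itself reports failures after lefamulin alone and successes after pre-treatment, which is the setting in which one arm might stop.

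Finally, a reader might infer that the total of 30 cannot be reached because patients would be randomised while interim results mature. That needs assumptions about accrual, waiting time and the absence of a pause. It is a separate question of interim timing, and the reference to the remaining 20 patients is consistent with a pause.

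**Conclusion.** The point holds within limits. If exactly one regimen is dropped, the label is wrong for 20 of 30 patients in two places. The comparison of regimens, as left open by the plan, would set about 10 patients in a stopped arm against about 30, of whom two thirds are neither randomised nor concurrent. The effect is a shift of two thirds of any drift between stages, plus an interval that is too narrow for the randomised evidence. The drift and the cure rates in the illustration are assumptions. The probability of reaching this situation runs from about 10% to 63% over the true cure rates considered. Restricting the comparison to concurrent patients removes the drift but not the selection created by the futility stop, which is about as large either way (33.2 and 34.5 points when both regimens cure 60%).

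**What to change.** 1. In Study Design and in the Table 2 caption, describe the 30 as about 10 randomised plus 20 directly assigned.
2. In Data analysis, prespecify that the regimen comparison uses only patients randomised while both arms were open. The directly assigned patients contribute only to the retained regimen's single-arm estimate and confidence interval, for which the N=30 limits in Table 2 stand.
3. State that, if an arm was dropped, the comparison is descriptive and the futility stop biases it against the dropped arm, since step 2 does not remove that selection.

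These are a few sentences, best settled before interim results are seen so that the comparison set is not chosen with the data in view. The cost is a wider interval for the comparison when an arm is dropped: 7 to 74 instead of 15 to 72 in the illustration.

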# Study population:

Symptomatic patients with MG treatment failure will be eligible. Treatment failure will be defined as persistent symptoms and a positive NAAT test after (a) moxifloxacin and/or (b) other second or third line antimicrobials (e.g., minocycline, omadacycline, other), or (c) when moxifloxacin is contraindicated. Additional inclusion and exclusion criteria are:

# Inclusion Criteria:

- Physician referral
- Persistent symptomatic urogenital MG infection documented by any NAAT 14-90 days after completion of the prior antimicrobial regimen for MG
- Low risk of reinfection defined as no unprotected sex with an untreated sex partner since completion of the prior antimicrobial regimen
- Male or female sex at birth
- ≥18 years of age
- English-speaking
- Able to provide written informed consent
- Able to undergo a test to confirm MG infection at baseline and tests of cure 21-28 days and 42-47 days after completing lefamulin

- Referring physician willing and able to provide needed patient information
- Living in the US

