## Tests of cure

Tests of cure will be performed in the UW Global Health STI Laboratory (laboratory director [name]). The Hologic Aptima MG assay, which we propose to use for tests of cure, has higher sensitivity and specificity than most other assays. Thus, test-of-cure windows when using this assay are generally longer (21-28 days) than when other assays are used. Furthermore, instances of MG recrudescing after an initial negative test subsequent to treatment have been reported, suggesting that additional follow-up after an initial test of cure is warranted in studies of novel antimicrobials. Therefore, we will perform two tests of cure (one at 21-28 days and one at 42-47 days after completion of lefamulin).

The research coordinator will ship Aptima test kits to enrolled patients, one 21-48 days, and one 42-47 days after completion of Lefamulin. In addition to the Aptima collection kit and instructions and shipping materials to return the Aptima tubes to the UW Global Health STI Laboratory, that package will also include materials and instructions for culture specimen collection as described above. Culture specimens will be shipped at the same time as the test of cure specimens.

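### The pre-treatment MG test is collected but never used, so a patient who qualified early and was already clearing from the prior drug counts as a lefamulin cure

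*Combined protocol and SAP*

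**What the plan says.** **Entry.** The Inclusion Criteria require "Persistent symptomatic urogenital MG infection documented by any NAAT 14-90 days after completion of the prior antimicrobial regimen for MG". The Study population section asks for both symptoms and a test: "Treatment failure will be defined as persistent symptoms and a positive NAAT test after (a) moxifloxacin", and so on for the other drug categories. It sets no minimum interval of its own.

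**Which assay.** Any NAAT qualifies. The Background says that "only two nucleic acid amplification tests (NAAT) are currently approved by the FDA: the Hologic Aptima MG assay and the Roche TV/MG test", so Aptima is a foreseeable entry test.

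**How lefamulin is judged.** The Tests of cure section says that the Aptima assay "has higher sensitivity and specificity than most other assays" and draws the consequence: "Thus, test-of-cure windows when using this assay are generally longer (21-28 days) than when other assays are used". The primary outcome is a negative Aptima result in that 21-28 day window.

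**The baseline specimen.** The Inclusion Criteria ask that the patient be "Able to undergo a test to confirm MG infection at baseline"; the Exclusion Criteria mirror this. Ability and willingness are required, but a positive result is not. The dispensing section puts the collection kit in the medication package, after consent and prescription, and names no assay for it.

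**Who is counted.** The Outcomes section does not make cure conditional on a positive baseline test. The Data analysis section uses as denominator everyone with data on the outcome in question. The futility rule counts cures among the first ten patients in each arm, again with no baseline condition.

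**The concern.** The plan applies different waiting times to the same assay. A positive Aptima result on days 14-20 after the prior drug can document that this drug failed, although the plan's general window for judging a drug by Aptima opens at day 21. Some patients who enter this way may have an infection that is resolving, or nucleic acid left over from one that has resolved. They can be negative by the time of the lefamulin test of cure whatever lefamulin did.

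The baseline specimen is the natural safeguard, but as written it protects nothing. A patient whose baseline test is negative still enters the denominator and, if negative again later, the numerator.

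The objective is efficacy in treatment failures, and neither arm is untreated. Carry-over from the prior drug is therefore credited to lefamulin in each arm's cure rate and in the rule that decides whether a regimen is dropped.

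**Working it through.** **Inputs from the documents.** Entry window 14-90 days; Aptima window 21-28 days; futility if 3 or fewer of 10 are cured; benchmark efficacy 60%; Table 2 with 17 of 20 cured.

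**Assumed input.** f, the fraction of analysed patients who would test negative regardless of lefamulin. The documents do not give it.

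**Step 1: reproduce the plan's own figures.** Exact binomial P(X ≤ 3 | n = 10, p = 0.60) = 0.0548, which agrees with the stated 5%. The exact interval for 17/20 is 62.11-96.79%, as in Table 2.

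**Step 2: a plausible range for f.** For the early-test route, f is the product of three shares: qualified on days 14-20, tested with Aptima, and actually clearing.

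- If qualifying tests were spread evenly over days 14-90, the first share is 7/77 = 9.1%. That would be the ceiling for f by this route.
- If half of those tests were Aptima and half of those patients were clearing, f = 0.091 × 0.5 × 0.5 = 2.3%.
- Clustering of tests soon after day 14 would raise f. The documents do not describe the timing.

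A range of 2-10% covers these cases.

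**Step 3: effect on the cure rate and on stopping.** Apparent cure = f + (1 − f)p. The excess over the true rate p is f(1 − p), which cannot be negative.

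| f | True 60% reads | True 30% reads | P(≤ 3 of 10) when true rate is 30% |
|---|---|---|---|
| 0 | 60.0% | 30.0% | 65.0% |
| 2% | 60.8% | 31.4% | 61.2% |
| 5% | 62.0% | 33.5% | 55.5% |
| 10% | 64.0% | 37.0% | 46.0% |

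**Step 4: effect on the precision claim.** The Sample size section relies on a lower limit above 60% in an arm of 20. Take the 17/20 row and remove spurious cures from both numerator and denominator:

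- none removed, 17/20: exact lower limit 62.1%
- one removed, 16/19: 60.4%
- two removed, 15/18: 58.6%

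**Step 5: effect on the comparison of regimens.** If f is the same in both arms, the difference becomes (1 − f)(p_B − p_A). It shrinks by the factor 1 − f, for example 0.90 at f = 10%, and keeps its sign. The main damage is to the single-arm cure rates and the futility count.

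**The case against.** A reader might infer that entry rests on the NAAT alone, that Aptima cannot be interpreted before day 21, and that a large share of the reported cures could be spurious. The documents do not support these readings.

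- **Symptoms are also required.** A patient whose infection is resolving must still be symptomatic to enter, which narrows the group. It does not empty it, since nothing in the plan says that symptoms separate failure from slow resolution.
- **The window statement is general.** The plan calls Aptima windows generally longer. It gives no false-positive rate before day 21 and does not call an earlier positive uninterpretable. It also implies shorter windows for other assays, so a 14-day floor for any NAAT is not a contradiction in itself. The tension is confined to Aptima, or an unrecorded assay, on 7 of the 77 eligible days.
- **The baseline swab will usually come later than day 20.** The laboratory result, referral, consultation, consent, pharmacy check and shipping all precede it. A baseline specimen that is itself too early is therefore unlikely, although no durations are given. This makes the baseline result more informative. It does not help while no rule uses that result.
- **The size is not anchored.** An f of 10-20% of all entrants has no source in the documents, and with evenly spread testing the early-test route could not exceed about 9%.
- **Access matters.** Care is decentralised and this is a compassionate-access study, so accepting outside tests is a defensible practical choice. Delaying entry would be a real cost to patients.

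What stands is that the two windows are not reconciled, and that no section says how a patient with a negative baseline test is handled in the efficacy analysis or the interim count.

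**Conclusion.** The point holds as a gap in the analysis definition. As written, a patient who had cleared before the first dose counts as a lefamulin cure in the primary estimate and in the futility count. The unreconciled entry and test-of-cure windows make such patients more likely.

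The direction is certain under the model used, in which affected patients test negative whatever lefamulin does. The size is not known. For f between 2% and 10%, a true 60% gains roughly 1 to 4 points, and the chance of stopping a 30%-effective regimen falls by roughly 4 to 19 points. Effects of this order are modest, but with 10 patients per arm at the interim and 20 or 30 at the end, one or two misclassified patients can matter.

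The documents do not show that any patient is misclassified, and they do not support a claim that the trial's cure rates will be badly inflated.

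**What to change.** 1. In Outcomes, Criteria for futility and Data analysis, define the primary and interim efficacy denominators as patients whose pre-treatment baseline specimen is MG-positive. Name the assay used for that specimen and state that it is collected before the first dose of any study antibiotic. Because it precedes treatment in both arms, conditioning on it does not disturb the randomised comparison. The futility threshold is set for ten patients, so apply it to the first ten baseline-positive patients in each arm.
2. Add a sensitivity analysis that excludes patients whose only positive results were from Aptima or an unknown assay before day 21 after the prior regimen. This covers the patient who is still positive at an early baseline test.
3. Record and report, for each patient, the assay of the qualifying NAAT and its interval from the end of the prior regimen.
4. Have the sponsor reconcile the entry window with the reasoning in the Tests of cure section. Whether entry changes is an eligibility and access decision for the sponsor.

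**Cost.** Items 1 to 3 need a few lines of analysis text and two recorded fields. A few patients leave the efficacy denominator, so intervals widen slightly, and the interim count may fill a little later. Under items 1 to 3 no patient loses access to treatment.
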